10.3 Clinician-reported grip strength

Grip strength will be assessed by qualified site personnel according to the schedule of study assessments ([Table 5-1](#)). Qualified site personnel will be trained regarding obtaining and recording measurements. At each scheduled visit, the grip strength, generated by the study participant, and measured using a standardized tool, will be evaluated 3 times in the dominant hand. All 3 assessments will be recorded in the eCRF. For analyses, UCB will utilize the maximum of the 3 assessments. Efficacy will be assessed as change from Baseline in maximum grip strength score at each scheduled assessment during the Treatment and Observation Periods.

Study participant experienced CIDP relapse (maximum grip strength) (defined as a clinically important deterioration from Baseline in grip strength, ie, a decline of >14kPa) up to Week 25 after first treatment and time to CIDP relapse (maximum grip strength) during the Treatment Period will be assessed together with the change from Baseline in maximum grip strength score at each scheduled assessment during the Treatment and Observation Periods.

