4.2 Handling of dropouts or missing data

4.2.1 Efficacy data

For study participants who prematurely withdraw for any reason before Visit 26, data collected during the PEOT Visit will be mapped to the closest missing visit according to the visit schedule utilizing the relative day in study to a maximum of Visit 26 (end of treatment period). However, if a participant receives rescue medication prior to the PEOT visit, any efficacy assessment post intake will be regarded invalid and only listed. Assessments on the same day as first intake of rescue medication are acceptable for analysis.

Study participants administered an Ig infusion rescue medication during the treatment phase will be considered relapsed even in case no relapse was documented. Missing relapse data, i.e. data for any relapse event definition, will be considered missing. In case of drop-out, if no relapse occurs or rescue medication is taken until PEOT visit (inclusively), the subject will be censored for time-to-event analysis at the date of PEOT visit.

Participants are asked to record three grip strength score assessments at each day. The efficacy parameter will be derived from grip strength scores taken by a participant up to five days prior to the first IMP (for Baseline value) or visit date (for post Baseline visit value):

1. Maximum of grip strength assessments available at a particular day
2. Mean of maximum grip strength over most recent three non-missing days - up to a maximum of five days
3. Missing values: In case all three assessments of a day are missing, the maximum grip strength score will be set to missing and will not be used for the derived score. In this case the preceding day's maximum grip strength score will be used instead, but no later than the fifth day prior to the first IMP or visit date respectively. In case data is entirely missing during the last five days prior to the visit, the derived score will be set to missing.

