6.2 Other Baseline characteristics

The prior Ig treatments taken four months before the Baseline visit in CIDP04 will be listed for the SS by treatment group for all study participants and will include the reported term, preferred term (PT), dose, route of administration, frequency, formulation, start/stop dates and duration (in days) and if it was a rescue treatment in the parent study or not. For definition of prior treatments see [Section 6.4.1](#).

Duration will be calculated as follows:

$$\text{Duration (in days)} = (\text{End date of Ig treatment} - \text{Start date of Ig treatment}) + 1$$

In addition, the following variables will be listed and summarized at baseline for the SS by treatment group:

- iRODS score (raw sum score, logit locations and centile metric scores)
- INCAT
- Grip strength (assessed by site personnel and patient reported grip strength)
- Immunological variables (IgG [including total IgG and IgG subclasses], IgM, IgA, IgE)
- Cytokines
- Serum (C3 and C4) and plasma complement levels (C3a and C5a)

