8.3 Maximum Grip Strength (Assessed by Site Personnel)

8.3.1 Maximum Grip Strength (Assessed by Site Personnel)

Grip strength is assessed by qualified site personnel at each scheduled assessment. Qualified site personnel will be trained regarding obtaining and recording measurements. At each scheduled visit, the grip strength, generated by the participant, and measured using a standardized tool, will be evaluated 3 times in the dominant hand. All 3 assessments will be recorded in the eCRF and listed. For analyses, UCB will utilize the maximum of the 3 assessments, which will be flagged in listings.

Maximum grip strength as assessed by site personnel will be listed and summarized by treatment group for each scheduled assessment during the Treatment and Observation Period together with changes from baseline.

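### SAP 4.2.1 derives grip strength from daily participant recordings that CIDP04 does not schedule, in conflict with the site-measured maximum in SAP 8.3.1

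*SAP*

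**What the plan says.** SAP 4.2.1, on missing efficacy data, ends with a grip-strength rule. It opens: "Participants are asked to record three grip strength score assessments at each day". It continues: "The efficacy parameter will be derived from grip strength scores taken by a participant up to five days prior to the first IMP" for the Baseline value, with the visit date as the anchor for post-Baseline values. Three steps follow: take the largest reading on each day; then "Mean of maximum grip strength over most recent three non-missing days - up to a maximum of five days"; and finally "In case data is entirely missing during the last five days prior to the visit, the derived score will be set to missing".

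SAP 8.3.1 defines the endpoint differently: "Grip strength is assessed by qualified site personnel at each scheduled assessment", three times in the dominant hand, and "For analyses, UCB will utilize the maximum of the 3 assessments, which will be flagged in listings". Protocol 10.3 agrees: "Grip strength will be assessed by qualified site personnel according to the schedule of study assessments", with the maximum of the three readings analysed. SAP 2.2.2.1, 8.3.2 and 8.3.3 and the Baseline definitions in SAP Table 3-1 also name site personnel.

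The only grip row in protocol Table 5-1 is the site-personnel one. The home-visit procedures in protocol section 8 contain no grip measurement, and the ordered list of patient-reported outcomes in protocol 10.4 does not include grip.

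SAP 3.9, which lists changes to the protocol-defined analyses, includes the added 8 kPa threshold but not a new grip derivation. Outside 4.2.1, the one mention of participant data is in the list of baseline characteristics in SAP 6.2: "Grip strength (assessed by site personnel and patient reported grip strength".

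**The concern.** The SAP contains two rules that can both be read as the derivation of the grip endpoint, and one of them needs data that CIDP04 does not schedule. Section 4.2.1 calls its result the efficacy parameter, covers both Baseline and post-Baseline values, and is where a programmer looks for missing-data handling.

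Grip feeds two relapse definitions (a decline of more than 14 kPa and of more than 8 kPa). The 14 kPa criterion also enters the composite relapse in SAP 8.4. Two programmers working from this SAP could therefore produce different grip results, or one of them could produce none.

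There is also a gap. Because 4.2.1 deals only with participant recordings, the SAP has no rule for a visit at which only one or two of the three site readings were obtained.

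**Working it through.** The documents give no numerical figure on this point, so there is nothing to reproduce. The check compares the two rules and then applies 4.2.1 to the grip schedule.

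**Comparison of the rules**

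| | SAP 4.2.1 | SAP 8.3.1 and protocol 10.3 |
|---|---|---|
| Who records | Participant | Qualified site personnel |
| When | Each day, in the five days before first IMP or the visit | At the scheduled visit |
| Statistic | Mean of up to three daily maxima | Single maximum of three readings |
| If no data | Score set to missing | Not stated |
| Scheduled in CIDP04 | No | Yes (Table 5-1) |

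The rules differ in source, window and statistic.

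**Scheduled post-Baseline grip assessments** (Table 5-1 and protocol section 8)
- Part 1: Weeks 2, 3, 4, 5, 7, 9, 13, 17 and 21, which is 9.
- Part 1 only, adding Weeks 25 and 32: 9 + 2 = 11.
- Parts 1 and 2, adding every fourth week from 25 to 73 (13 visits) and Weeks 77 and 84: 9 + 13 + 2 = 24.

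These are full-schedule counts. A participant who stops early or enters an Access Program has fewer, but the proportions below do not change.

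**Applying 4.2.1**
- *Participant recordings only, as written.* The window is always empty after Baseline, so the third step makes the score missing: 11 of 11, or 24 of 24. No post-Baseline change in grip exists, and neither measured threshold can be tested.
- *Site readings put through the same rule, visit day not counted.* The closest site assessments are nominally 7 days apart, outside the five-day window: 24 of 24 missing. The visit windows allow doses as little as 5 days apart. In that case the previous visit's reading would fall in the window and stand in for the current one, which is also not intended.
- *Site readings, visit day counted.* One day contributes, so the mean of daily maxima equals that day's maximum: 0 of 24 missing, and the result is the SAP 8.3.1 value.

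**Applying SAP 8.3.1 instead**

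All 11 or 24 scores can be derived whenever the assessment is done.

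**What survives on the worst reading**
- SAP 4.2.1 counts a participant given Ig rescue during treatment as relapsed even if no relapse was documented. SAP 8.1.2 treats rescue as relapse, and SAP 8.3.2 and 8.3.3 adopt its methods. Rescue-based events therefore remain.
- The composite in SAP 8.4 keeps iRODS, adjusted INCAT and the investigator's other relapses.

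**The case against.** The strongest reply is that 4.2.1 does not govern the endpoint at all. Every section that defines the grip variable names site personnel, and SAP 8.3.1 gives a complete rule for a visit with three readings. By its own terms 4.2.1 concerns scores taken by a participant, and SAP 6.2 treats patient-reported grip as something distinct from site grip. On that reading the paragraph is a stray rule for a separate measure and the site scores are untouched. Grip is also one of the other efficacy variables, summarised descriptively in a single-arm extension whose primary variable is treatment-emergent adverse events.

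Much of this stands. The loss of scores occurs only if 4.2.1 is allowed to override 8.3.1, and a reader who inferred that the grip endpoint is simply lost would go beyond the text.

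It does not clear the paragraph. Neither document defines a patient-reported grip variable, the rule expressly covers post-Baseline visits for which no such data are scheduled, and it leaves site readings without a missing-data rule.

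A reader might also infer that, for previously treated participants, a patient-recorded CIDP01 Baseline would be compared with site-measured follow-up. The documents do not support that. SAP Table 3-1 fixes the efficacy Baseline as site-assessed grip, SAP 8.3.2 and 8.3.3 define deterioration on site measurements, and SAP 6.2 only lists and summarises baseline characteristics.

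**Conclusion.** The SAP is wrong as written on this point. The grip rule in 4.2.1 has no post-Baseline data source in CIDP04, conflicts with SAP 8.3.1 and protocol 10.3, and is not declared as a change.

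The size depends on how 4.2.1 is read:
- Applied to the endpoint, it makes all post-Baseline CIDP04 grip scores missing (11 or 24 per participant on the full schedule) and removes the measured 14 kPa and 8 kPa criteria.
- Read as a rule for a separate measure, it has no effect after Baseline, and the remaining defect is the absent rule for incomplete site readings.

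The statement about missing scores is limited to post-Baseline values. For previously treated participants Baseline lies in CIDP01, and for direct entrants the five days before Visit 2 fall within CIDP01. The documents do not say whether CIDP01 collected daily participant grip.

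The conclusion assumes that Table 5-1 and protocol section 8 list all grip data collected in CIDP04. The correction should be made before the grip outputs are programmed. It does not affect the primary safety analysis or membership of the FAS, which depends on iRODS.

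**What to change.** - **SAP 4.2.1:** delete the participant-recorded grip paragraph and its three steps.
- **SAP 4.2.1 or 8.3.1:** state that Baseline (as in Table 3-1) and every visit use the maximum of the available site readings, and that the score is missing only if all three readings are missing.
- **SAP 6.2:** state where patient-reported grip comes from. If CIDP01 collected it, keep it as a labelled descriptive item that is never used as the Baseline for change or relapse. If not, remove it.

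The cost is an edit to the SAP text. No new data, visits or protocol change are needed, because the replacement rule follows protocol 10.3.

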4.2.2 Safety Laboratory data

Measurements below the limit of quantification (BLQ) will be imputed with half of the lower limit of quantification (LLOQ) for the purpose of calculating change from Baseline and the respective descriptive statistics.

Measurements above the limit of quantification (ALQ), if applicable, will be imputed to the upper quantification limit for the calculation of changes from baseline and descriptive statistics. These rules will be applied to all safety laboratory data including clinical chemistry and urinalysis.

Descriptive statistics will be displayed if at most 33% of the individual data points at a timepoint are missing or are either not quantifiable (<LLOQ) or ALQ. Values that are BLQ will be replaced by the numerical value of the LLOQ/2 in this instance and values that are ALQ will be imputed to the value of the upper quantification limit. If more than 33% of the individual data points at a timepoint are missing or not quantifiable (BLQ and/or ALQ), no descriptive statistics will be presented.

4.2.3 Pharmacodynamic data

Measurements BLQ are not anticipated for the total serum IgG data. If any BLQ measurements are received, these will be regarded as missing for the presentation of descriptive statistics and changes from Baseline.

Descriptive statistics will be calculated if at most 33% of the individual data points at a timepoint are missing or are either not quantifiable (<LLOQ) or ALQ as described in [Section 4.2.2](#).

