4.2.4 Immunological data

The rules for handling BLQ or ALQ measurements for all immunological data will be as described in [Section 4.2.2](#).

Descriptive statistics will be calculated if at most 33% of the individual data points at a timepoint are missing or are either not quantifiable (<LLOQ) or ALQ as described in [Section 4.2.2](#).

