4.2.5 Rozanolixizumab concentration data

Measurements that are BLQ will be imputed with half of the LLOQ for the purpose of calculating the geoMean and its 95% CI, the geoCV, the arithmetic mean, and SD for summaries

and figures. If any summary value (geoMean, arithmetic mean, lower CI level or minimum) is lower than LLOQ, then 'BLQ' will be displayed.

For the individual figures, any concentrations that are BLQ will be considered as missing, with the exception of predose BLQ measurements on Week 1/ Visit 2 for study participants treated with placebo in the parent study, which will be imputed with zero for linear scale plots.

Additional rules for PK data summaries are provided in Section 9.1.

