9.2.1 Total Serum IgG

Total Serum IgG concentrations and IgG subclasses will be listed by treatment group and timepoint including absolute changes from Baseline and percentage changes from Baseline. Descriptive summaries (including n, arithmetic mean, median, SD, minimum and maximum) will be presented by treatment group and timepoint and ADA status (6 categories; see Section 9.3.2) for absolute values, changes from Baseline and percentage changes from Baseline.

Study participant total Serum IgG will be plotted against planned time. Mean Serum IgG, mean change from Baseline and percentage change from Baseline will be plotted against planned time by treatment group.

For each study participant, the minimum value and maximum decrease (absolute and percentage) from Baseline in total serum IgG concentration during the study (using all available data up to cut-off point) will be listed. The minimum value and maximum decrease will be summarized by treatment group. If a decrease from Baseline in IgG is not observed in a given study participant, the maximum decrease will be reported as the smallest increase from Baseline.

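### SAP 4.2.3 would treat any total IgG value below the quantification limit as missing, which understates the drug effect whenever one occurs (contingency rule, minor)

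*SAP*

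**What the plan says.** SAP 4.2.3 (Pharmacodynamic data) opens with an expectation, "Measurements BLQ are not anticipated for the total serum IgG data", and then gives the contingency rule: "If any BLQ measurements are received, these will be regarded as missing for the presentation of descriptive statistics and changes from Baseline". Its second paragraph sets a display threshold, "Descriptive statistics will be calculated if at most 33% of the individual data points at a timepoint are missing or are either not quantifiable", and refers to Section 4.2.2. That section, on safety laboratory data, substitutes for BLQ values when the threshold is met: "Values that are BLQ will be replaced by the numerical value of the LLOQ/2 in this instance".

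The neighbouring sections also use LLOQ/2. For immunological data, SAP 4.2.4 states "The rules for handling BLQ or ALQ measurements for all immunological data will be as described in" Section 4.2.2. For drug concentration summaries, SAP 4.2.5 states "Measurements that are BLQ will be imputed with half of the LLOQ".

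SAP 9.2.1 lists and summarizes, for each participant, "the minimum value and maximum decrease (absolute and percentage) from Baseline in total serum IgG concentration during the study". It says that all available data up to the cut-off are used. It does not say whether a BLQ result counts.

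**The concern.** Rozanolixizumab is developed to reduce IgG. A post-Baseline BLQ result is therefore not a lost observation. It is a known value lower than every quantifiable one, and treating it as missing is informative in one direction only: the visit mean goes up and the mean decrease goes down. The maximum decrease is a change from Baseline, so 4.2.3 covers it directly. The next lowest quantifiable value takes over and the decrease is understated.

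There is also a consistency problem. SAP 6.2 groups total IgG and its subclasses with the immunological variables, for which 4.2.4 prescribes LLOQ/2, while 4.2.3 prescribes missing. Within 4.2.3, one paragraph says missing and the next refers to a section that says LLOQ/2. Two programmers could produce different tables from this text. IgG subclasses and NF-L are pharmacodynamic variables too, but the BLQ sentences in 4.2.3 are introduced for total serum IgG only, so the rule for the others is unclear.

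**Working it through.** The plan gives no figure to reproduce. It states no IgG LLOQ, no expected IgG distribution and no expected number of BLQ values. What follows is illustrative, on assumed values.

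**Effect on a visit mean.** Assume lognormal IgG on treatment with median 2 g/L and CV 50%, and Baseline 10 g/L.

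- Log-scale SD: s = √ln(1 + 0.5²) = √ln 1.25 = 0.472.
- True mean: m = 2 × exp(s²/2) = 2.24 g/L, a reduction of 1 − 2.24/10 = 77.6%.
- With z = ln(LLOQ/2)/s (here 2 is the median), the BLQ share is Φ(z).
- Mean with BLQ dropped: m × Φ(s − z)/(1 − Φ(z)).
- Mean with substitution: Φ(z) × LLOQ/2 + m × Φ(s − z) (here LLOQ/2 is half the limit).

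| LLOQ (g/L) | z | BLQ share | Mean, true | Mean, BLQ dropped | Mean, LLOQ/2 | Reduction, true / dropped / LLOQ/2 |
|---|---|---|---|---|---|---|
| 0.5 | −2.93 | 0.2% | 2.24 | 2.24 | 2.24 | 77.6% / 77.6% / 77.6% |
| 1.0 | −1.47 | 7.1% | 2.24 | 2.34 | 2.21 | 77.6% / 76.6% / 77.9% |

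For LLOQ 1.0: 2.236 × 0.9738/0.9289 = 2.34, and 0.0711 × 0.5 + 2.236 × 0.9738 = 2.21. Dropping the values costs about 1 percentage point of mean reduction. LLOQ/2 errs by about 0.2 points the other way.

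**How often BLQ would occur.** With an assumed median of 2.5 g/L and CV 40% to 60%, the chance that a single value is BLQ is below 0.01% at an LLOQ of 0.3 g/L or less, 0.001% to 0.2% at 0.5 g/L, and 0.9% to 4.9% at 1.0 g/L.

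**Effect on one participant's maximum decrease.** Percentage decrease = 100 × (1 − value/Baseline). Take Baseline 10 g/L and LLOQ 0.3 g/L. The true maximum decrease lies between 97.0% and 100%, and LLOQ/2 gives 100 × (1 − 0.15/10) = 98.5%. With the BLQ value dropped, the reported decrease depends on the lowest quantifiable value:

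- 0.3 g/L: 97.0%, a gap of 1.5 points from LLOQ/2
- 1 g/L: 90.0%, a gap of 8.5 points
- 2 g/L: 80.0%, a gap of 18.5 points

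Over Baselines of 6 to 14 g/L and LLOQs of 0.1 to 1.0 g/L, the gap runs from 0.4 to 32.5 points. The top of that range needs a participant with no quantifiable value between 2 g/L and an LLOQ of 0.1 g/L. That is hard to reconcile with the weekly IgG checks below 2 in the protocol's Table 5-1 footnotes.

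**The case against.** The strongest reply is that the rule may never operate, since the SAP says BLQ values are not expected. That stands, and it sets the priority: this is a contingency rule, and the documents do not show that any drug effect will be lost. It does not defend the rule, which has an effect only when a BLQ value arrives and then acts in the wrong direction.

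Four stronger readings are tempting and are not supported.

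- *Very low IgG is foreseen, so BLQ values are too.* Protocol 6.4.1.3 acts on IgG below 1 g/L, but a low value is not the same as one below the assay limit.
- *The bias could be several points.* Means shift that much only with a high LLOQ, such as 1.5 g/L. Protocol 6.4.1.2 and 6.4.1.3 separate 1 to <2 g/L from <1 g/L, and SAP Table 13-2 marks IgG ≤1 g/L as abnormal. An assay that could not quantify below 1.5 g/L could not support those cut-offs.
- *Every affected participant gets a wrong nadir.* This is secure only for the maximum decrease. For the minimum, 9.2.1 is silent on BLQ. A BLQ value at Baseline would leave the change missing, not wrong.
- *Low-IgG safety information disappears.* The rule covers descriptive statistics and changes from Baseline. SAP 9.2 keeps listings for the whole Safety Set, and SAP 10.3 flags markedly abnormal values in listings.

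Two further qualifications are fair. LLOQ/2 is not universal elsewhere: the individual concentration figures in 4.2.5 mostly treat BLQ as missing. And pharmacodynamics is an exploratory objective with descriptive output, so no formal decision rests on these means.

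**Conclusion.** The point holds as a minor one. When triggered, the rule biases mean IgG upward and understates the maximum decrease, and it is inconsistent with the summary rules beside it. That direction needs only that a post-Baseline BLQ value lies below every quantifiable one. The size cannot be derived from the documents. On the assumed distribution (median 2 g/L, CV 50%, Baseline 10 g/L), the effect on mean reduction is negligible at an LLOQ of 0.5 g/L or less and about 1 percentage point at 1.0 g/L. In an affected participant the understatement of the maximum decrease may be trivial or substantial, depending on the neighbouring quantifiable values.

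**What to change.** In SAP 4.2.3, replace the sentence that regards BLQ values as missing with the LLOQ/2 rule of 4.2.2, and say that it applies to total IgG, IgG subclasses and NF-L. In SAP 9.2.1, state that a post-Baseline BLQ value counts as the participant's minimum and is shown as <LLOQ, and that the maximum decrease is then computed from LLOQ/2 and flagged as imputed.

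The cost is a sentence in each section, with no new data. The downside is that LLOQ/2 is an approximation and can slightly overstate the decrease (77.9% against a true 77.6% in the LLOQ 1.0 g/L example). The flag and the <LLOQ display keep that visible.
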